5.2.3. Product Storage

Study drug should be stored at room temperature. Study drug must be stored in a secure, environmentally controlled area that is monitored (manually or automatically) and accessible only to the Investigator and authorized study staff prior to dispensation to the participant. For additional information on product storage, please refer to the Pharmacy Manual.

5.2.4. Preparation and Administration

Participants will be taking between 1 and 6 tablets daily, depending on the dose and Cohort assignment. Participants can either swallow the tablet[s] whole or crush the tablet[s] and sprinkle on soft foods.

Cohorts 1 to 3 will receive doses QD. The dose will be taken with the evening meal. The first 2 weeks in Cohorts 1, 1a, and 2 will require dosing with a morning meal.

Cohorts 4-9 will receive BID dosing. Each dose should be taken with the morning and evening meal.

If necessary, the study drug may be taken up to 30 minutes after completing the meal(s) at home. If a participant has not consumed study drug within 30 minutes following the meal(s), the participant should consume study drug with a snack. Study drug will be dispensed at Day 1 for the duration of the study.

The Day 1 and Day 14 morning doses of tildacerfont will be administered in the clinic for Cohorts 1, 2, 4, 5, 6, 7, 8, and 9 (and 1a, if indicated) and Day 1 only for Cohort 3. Any remaining study drug will be returned for accountability at Visit 6 (Week 12) for Cohorts 1 to 3 and Visit 4 (Week 4) for Cohorts 4 to 9, any early termination (ET) Visits, and during extension visits. The Investigator is responsible for ensuring that dosing is administered in compliance with the protocol.

Preparation and administration instructions are included in the Pharmacy Manual.

5.3. Concomitant Therapy

Concomitant medication is any medication (including over-the-counter [OTC] medication, prescription medication, vaccines, vitamins, and supplements) that the participant is receiving at Screening or receives during the study. All concomitant medications must be recorded, along with:

- Reason for use
- Dates of administration, including start and end dates
- Dosage information, including dose and frequency.

All concomitant medications should be compared against the list of prohibited medications and the list of other medications of concern provided in [Appendix 3](#). Participants/guardians should be instructed to contact the site immediately any time a new medication is required during the course of the study, including prescription and OTC medications, even those to be used for only a short period of time (e.g., antibiotics, cold and flu remedies, GI therapies, opioids or other pain relievers). The MM should be contacted if there are any questions regarding concomitant or prior therapy.

5.3.1. Glucocorticoid Replacement Therapy

5.3.1.1. General Procedures for Glucocorticoids

Concomitant medications include GCs. Information to be collected at Screening about a participant's current and prior GC therapy for the past month include the type(s) of GC, the regimen(s), and any GC stress dosing during the past month.

To be eligible for this study, participants must be on a stable dose of GC replacement for ≥ 1 month before Screening without evidence of non-adherence (standard of care weight-based dose adjustments

and stress dosing are allowed). Participants with the salt-wasting form of CAH who take mineralocorticoids must also be on a stable dose of mineralocorticoid replacement for ≥ 1 month before Screening.

On the mornings of all study visits, including the Screening Visit, participants should delay taking any morning dose of GC medication. On Day 1 all participants will receive a supervised tildacortal dose in clinic and can take their morning GC dose at that time (after the pre-dose assessments). The same applies to Cohorts 1, 2, 4, 5, 6, 7, 8, and 9 (and 1a if indicated) for Day 14. On all other visits, participants can take their morning GC dose after completion of the 8 AM (± 1 hour) assessments (PK, PD, and safety). On all other non-clinic visit days during the study, participants should take their GC medication at the usual time(s). Mineralocorticoid may be taken at any time of day, but its timing relative to laboratory assessments should be consistent throughout the study.

5.3.1.2. A4-Based Glucocorticoid Dose Adjustment Algorithm

In all cohorts, GC dose (frequency, distribution of doses, or total daily dose) may be adjusted based on A4 levels at Weeks 4 (all participants Cohorts 1 to 3; and participants in Cohorts 4 to 9 if continuing in the extension) and 8 (all participants in Cohorts 1 to 3), and Week 12 (participants in Cohorts 1 to 3 if continuing in the extension period). In the extension, GC dose may be adjusted based on A4 levels at each visit. See the Pharmacy Manual for further guidance on GC dose adjustments.

The below A4-based algorithm will be used to guide changes to GC replacement therapy. Reductions below physiologic levels should be discussed with the MM.

A4 Level $\leq 1x$ ULN

- Reduce GC dose

A4 Level 1.0 to $\leq 1.5x$ ULN

- Maintain GC dose

A4 Level $> 1.5x$ ULN

- Increase GC dose

The Sponsor or designee may contact the site after Weeks 4, 8, and 12 (or any extension visit) to confirm GC dose adjustments (note: only Week 4 for Cohorts 4 to 9). The Investigator should contact the MM if the Investigator does not intend to follow A4-based GC dose adjustment algorithm at a visit.

If a change in GC is warranted by the A4 algorithm, sites will contact participants by telephone after receipt of results (within approximately 2 weeks) after each applicable study visit. If no GC dose adjustment is warranted based on the A4 level, the site does not need to contact the participant.

5.3.1.3. Stress Dosing of Glucocorticoids

During times of clinically significant physical stress such as intercurrent illness with fever, surgical procedures, or significant trauma, participants may take extra GC consistent with the “sick day guidelines” for prevention of adrenal crisis shown in [Table 3 \(Bornstein 2016\)](#). The stress doses suggested in [Table 3](#) are based on published, clinical best practice. However, management of stress dosing of GCs is ultimately at the discretion of the Investigator and/or inpatient managing physician (if hospitalized). The GCs received during a stress dosing period during the study will be captured as concomitant medications while the stress itself should be captured as an AE.

If stress dosing occurs, the MM should be consulted on how this will affect the study visit schedule and continued participation in the study.

Table 3. Sick Day Guidelines for Stress Dosing of Glucocorticoids

Condition	Stress Dosing
Home management of fever >38 °C (>100.4 °F) or illness requiring bed rest, when requiring antibiotics for an infection, or before undergoing a minor outpatient procedure (e.g., dental work)	
 Approximately double the routine oral GC dose (and give as HC) until recovery (usually 2 to 3 days) For fever >39 °C (102.2°F) only, approximately triple the routine oral GC dose (and give as HC) until recovery (usually 2 to 3 days). Increase consumption of electrolyte-containing fluids and simple and complex carbohydrates (El-Maouche 2018), as tolerated.
Unable to tolerate oral medication due to gastroenteritis or trauma	
 HC 50 mg/m² IM (approximately 50 mg HC for school-age children, 100 mg HC for adolescents)
Minor to moderate surgical stress	
 HC 50 mg/m² IM or double or triple the routine oral GC dose (usually 1 to 2 days)
Major surgery with general anesthesia, trauma, or disease that requires intensive care	
 HC 50 mg/m² IV, followed by HC 50 to 100 mg/m² per day divided every 6 hours Weight-appropriate continuous IV fluids with 5% dextrose and 0.2% or 0.45% NaCl Rapid tapering and switch to oral regimen depending on clinical state
Acute adrenal crisis	
 Rapid bolus of normal saline (0.9%) 20 mL/kg. Can repeat up to a total of 60 mL/kg within 1 hour for shock HC 50 to 100 mg/m² bolus, followed by HC 50 to 100 mg/m² per day divided every 6 hours For hypoglycemia: 0.5 to 1 g/kg dextrose or 2 to 4 mL/kg of D25W (maximum single dose 25 g) infused slowly at rate of 2 to 3 mL/min. Alternatively, 5 to 10 mL/kg of D10W for children <12 years of age Cardiac monitoring: rapid tapering and switch to oral regimen depending on clinical state

Abbreviations: D10W=dextrose 10%; D25W=dextrose 25%; GC=glucocorticoid; HC=hydrocortisone; IM=intramuscular; IV=intravenous.

To prevent hypoglycemia, the participant should drink small amounts of clear sugar-containing liquids frequently and/or consume carbohydrates if the participant is able, glucose monitoring should be considered, and IV sodium and glucose replacement may be required ([Clayton 2002](#), [Merke and Bornstein 2005](#), [Han 2014](#)).

Day-to-day physical or psychological stressors, such as a short-term strenuous activity or school examinations, do not require increased GC dosing ([Clayton 2002](#), [Crown and Lightman 2005](#), [Merke and Bornstein 2005](#)).

Participants will maintain stress dosing until symptoms subside (or according to the clinical judgment of the treating physician), then return to his/her usual GC regimen.

5.3.2. Prohibited Concomitant Medications

- Use of other investigational drugs and devices are prohibited during the study.
- Rosiglitazone, testosterone, growth hormone, or any other medication or supplement that could impact participant safety or confound interpretation of study results are prohibited.

- Moderate to strong inhibitors and/or inducers of cytochrome P450 3A4 (CYP3A4); this includes consumption of grapefruit, grapefruit juice, or any foods that are known to be strong CYP3A4 inhibitors from 1 day before the first dose of study drug until after the final dose.
- Sensitive substrates or narrow-therapeutic-range substrates of CYP3A4 (e.g., dexamethasone and oxycodone)
Note: This does NOT apply to hormonal contraception containing ≤20 mcg ethinyl estradiol.
- Sensitive substrates or narrow-therapeutic-range substrates of BCRP (except those that can be administered QD in the morning, separated by approximately 10 hours from evening administration of study drug)

[Appendix 5](#) provides a non-exhaustive list of medications, including many commonly used medications, which are prohibited because of their potential for metabolic interactions with tildacerfont. It is critical that each participant's concomitant medications are carefully compared to the list in [Appendix 5](#).

6. STUDY DRUG DISCONTINUATION AND PARTICIPANT WITHDRAWAL

6.1. Study Drug Discontinuation

Participants and/or their parent/guardian may voluntarily discontinue study drug at any time. The Investigator and/or Sponsor may also discontinue a participant's study drug at any time. When feasible, Investigators should discuss any safety concerns with the MM as soon as possible to determine whether a participant should continue or discontinue study drug. Study drug will be discontinued in participants who experience individual treatment-stopping criteria described within this section. The Sponsor and Investigator will make efforts (when possible) to continue to collect data on participants who discontinue study drug.

If study drug is discontinued, the Investigator will report the discontinuation to the MM, document the date and reason for study drug discontinuation on the appropriate electronic case report form (eCRF), schedule an ET visit for the participant (see the Schedule of Activities in [Appendix 1](#), [Appendix 2](#), [Appendix 3](#), and [Appendix 4](#)) provide or arrange for appropriate follow-up, and document the course of the participant's condition.

Participants who prematurely discontinue study drug may be replaced at the discretion of the Sponsor to ensure adequate numbers of evaluable participants.

6.1.1. Dose-Limiting Toxicity Stopping Criteria

A DLT is defined as a Common Terminology Criteria for Adverse Events (CTCAE) Grade 3 or higher treatment-emergent adverse event (TEAE) considered at least possibly related to study drug. If a participant experiences a DLT, study drug will be discontinued. DLTs are clinically significant AEs (see [Section 6.1.7](#)).

6.1.2. Safety Monitoring and Stopping Rules for Abnormal Liver Chemistry Measurements

The following was adapted in accordance with the non-binding recommendations contained within the FDA Guidance for Industry Drug-Induced Liver Injury: Pre-marketing Clinical Evaluation, from the U.S. Department of Health and Human Services in July 2009.

Special attention is paid to potential liver toxicity because tildacerfont was identified as a bile salt export pump (BSEP) inhibitor based on pre-clinical studies. Although in vitro BSEP inhibition does not reliably predict in vivo BSEP inhibition, Spruce believes that the pre-clinical findings warrant ongoing clinical monitoring ([Jonathan 2018](#)). Consequently, abnormal transaminase results will be assessed as follows.

If stopping criteria are met at any time during the Treatment Period, study drug should be held until confirmatory testing of the transaminase, with additional measurements of total bilirubin, alkaline phosphatase (ALP), complete blood count (CBC) with differential and international normalized ratio (INR), is performed. Ideally, confirmatory testing would be performed within 48 hours of the initial receipt of the abnormal result. Confirmation testing through the central lab is preferred, but local laboratory testing may be necessary in certain circumstances. Confirmed cases meeting stopping criteria will be reported as an AESI and in cases where a possible Hy's Law case is present, the event should also be reported as an SAE. [Table 4](#) outlines specific stopping criteria for this study.

Table 4. Stopping Criteria and Increased Monitoring for Liver Chemistry Elevations

Criteria		Actions
Participant has symptoms (new or worsening) believed to be related to liver injury or hypersensitivity ¹		Hold study drug, measure liver chemistry (AST/ALT/ALP), CBC with differential, total bilirubin, total bile acids and INR as soon as possible and notify Sponsor.
ALT 3x ULN		Discontinue study drug and notify Sponsor.
ALT 3x ULN	AND total bilirubin 2x ULN (>35% direct bilirubin) ²	Discontinue study drug and notify Sponsor. Possible Hy's Law case— report as an AESI and SAE .
	AND INR >1.5	Discontinue study drug and notify Sponsor. Possible Hy's Law case— report as an AESI and SAE .
Total Bile Acids >5xULN		Discontinue study drug and notify Sponsor.

Abbreviations: AESI=adverse event of special interest; ALP=alkaline phosphatase; ALT=alanine aminotransferase; AST=aspartate aminotransferase; CBC=Complete Blood Count, INR=international normalized ratio; SAE=serious adverse event; ULN=upper limit of normal.

¹Symptoms related to liver injury include fatigue, nausea, vomiting, right upper quadrant pain or tenderness, and jaundice.

Symptoms related to hypersensitivity include fever, rash, and eosinophilia. Due to similarities in symptoms with adrenal insufficiency, clinical judgement will be required to assess likelihood that symptoms may be hepatic in origin.

²If serum bilirubin fractionation is not immediately available, discontinue study drug if ALT 3x ULN and bilirubin 2x ULN and record the presence/absence of detectable urinary bilirubin on dipstick, which is indicative of direct bilirubin elevations suggesting liver injury.

Investigation of the underlying cause of these transaminase elevations should include, but is not limited to:

- A detailed history of symptoms as well as current and prior medical diseases, especially biliary tract disease, co-morbid conditions associated with development of nonalcoholic steatohepatitis, and cardiovascular disease that would compromise adequate blood supply to the liver
- Examination of concomitant drug use (inclusive of OTC, herbal/dietary supplements, alcohol and recreational drug use)
- Environmental and chemical exposures
- Serology testing, as appropriate, based on laboratory findings, clinical exam and exposure history (i.e., viral hepatitis, Epstein Barr virus)
- Additional investigations as appropriate such as gastrointestinal (GI)/hepatology consultation, imaging studies or other laboratory testing may be performed at the discretion of the Investigator, in consultation with the Sponsor MM.

6.1.3. Laboratory Monitoring of Liver Function

- Monitor liver enzymes, total bilirubin, total bile acids, and INR at least two times a week until transaminase levels are <3x ULN, total bile acids are <5x ULN, total bilirubin <2xULN, and INR ≤1.5x ULN or levels stabilize, and the participant is asymptomatic.
- Obtain additional tests to evaluate liver function, such as fractionated bilirubin, as deemed appropriate.

- Thereafter, repeat testing will be performed as appropriate for the clinical circumstance until resolution or stability of transaminase values, total bilirubin, total bile acids and INR is achieved and any symptoms, if present, have abated.

In the event that study drug is discontinued, the decision to rechallenge will be made on a case-by-case basis and will require written approval by the Sponsor.

6.1.4. QT Stopping Criteria

Study drug will be discontinued for a participant if either of the following criteria is met:

- QTcF >500 msec OR uncorrected QT >600 msec
- Change from Screening in QTcF of >60 msec

One repeat ECG should be performed to confirm the accuracy and persistence of an initial result that fulfills the QT stopping criteria.

6.1.5. Suicidality Stopping Criteria

Tildacerfont is a central nervous system (CNS)-active drug. Some CNS-active drugs may be associated with an increased risk of suicidal ideation in certain populations. Although tildacerfont has not been shown to be associated with an increased risk of suicidal thinking or behavior in past clinical studies, participants will be monitored for such events during this study using the C-SSRS. Any participant who exhibits Suicidal Behavior or Suicidal Ideation in their responses on the C-SSRS, will have study drug immediately discontinued and should be evaluated by a psychiatrist. This safety finding will be considered an AESI if it is not an SAE (e.g., requiring hospitalization) (see [Section 7.2.8](#)).

6.1.6. Depression or Anxiety Stopping Criteria

Participants will be monitored for depression and anxiety during the study using the Patient Reported Outcomes Measurement Information System (PROMIS) Pediatric SF (Short Form) v2.0, the PROMIS Parent-Proxy SF (Short Form) v2.0, or the Survey of Well-Being of Young Children (SWYC). The questionnaire used will depend upon the participant's age. Any participant who develops severe depression or anxiety (CTCAE Grade 3 or higher), as assessed by the Investigator, will require study drug discontinuation and appropriate follow-up. This will be considered an AESI and if seriousness criteria are met, also reported as an SAE (e.g., requiring hospitalization) (see [Section 7.2.8](#)).

6.1.7. Clinically Significant Adverse Events

Clinically significant AEs include but are not limited to SAEs, AEs leading to study drug discontinuation/study withdrawal (e.g., based on stopping criteria in [Section 6.1](#)), DLTs ([Section 6.1.1](#)), and AESIs ([Section 7.2.8](#)). The occurrence of any clinically significant AE will be reported to the DMC on an ongoing basis.

The Investigator should consider study drug discontinuation and appropriate safety follow-up for a participant who experiences a potentially clinically significant AE. When feasible, the Investigator should contact the MM to discuss the participant's clinical condition before discontinuing study drug.

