3.1.1. Data Monitoring Committee

An independent DMC will review the available data on an ongoing basis throughout the study and before initiating a new cohort. The DMC will be composed of independent reviewers who are not involved in the conduct of the study. The DMC will advise the Sponsor of any trends or safety issues that may impact the study or study participants. In particular, the occurrence of any clinically significant AE (including but not limited to SAEs, AEs leading to study drug discontinuation/study withdrawal, dose-limiting toxicities [DLTs], and adverse events of special interest [AESIs], all considered at least possibly related to study drug) will receive special consideration (see [Section 7.2.5](#)). The Sponsor will make final decisions concerning the continuation, modification, or termination of the trial. The DMC's scope of responsibility, membership, confidentiality, and procedures will be established in a separate DMC charter. Three DMC reviews are planned during and upon completion of Cohorts 1-3. Three additional DMC reviews are planned during Cohorts 4-9. Ad hoc DMC meetings may be called by the Sponsor or the DMC Chair ([Figure 2](#)).

For Cohorts 1-3, the DMC will review safety data from a minimum of 2 sentinel participants for 2 weeks at each meeting. For Cohorts 4-9, the DMC will review safety data from a minimum of 4 sentinel participants at each meeting, but it is not required that 2 come from each cohort. However, to initiate a

new dosing regimen in a pediatric cohort, data from at least 2 pediatric sentinels must be included in the review.

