6.1.8. Dose Limiting Toxicity

If 2 participants in a cohort meet individual stopping criteria, the entire cohort will be stopped or dose-reduced.

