PROBABLY RELATED: This category applies to those AEs that the Investigator thinks are related to the study drug with a high degree of certainty. An AE may be considered probably related if or when it meets three of the following criteria : (1) it follows a reasonable temporal sequence in relation to administration of the study drug; (2) it could not be reasonably explained by the known characteristics of the participant's clinical state, environmental or toxic factors, or other therapies administered to the participant; (3) it disappears or decreases on cessation or reduction in dose of study drug. There are exceptions when an AE does not disappear upon discontinuation of the study drug yet drug-relatedness clearly exists (e.g., as in bone marrow depression, fixed drug eruptions, or tardive dyskinesia); or (4) it follows a known pattern of response to the study drug.
DEFINITELY RELATED: This category applies to those AEs that the Investigator thinks are incontrovertibly related to the study drug. An AE may be assigned an attribution of definitely related if or when it meets all of the following criteria : (1) it follows a reasonable temporal sequence in relation to administration of the study drug; (2) it could not be reasonably explained by the known characteristics of the participant's clinical state, environmental or toxic factors, or other therapies administered to the participant; (3) it disappears or decreases upon cessation or reduction in dose of study drug and recurs with re-exposure to the study drug (if rechallenge occurs); and (4) it follows a known pattern of response to the study drug.

Abbreviation: AE=adverse event.

The Investigator will use clinical judgment and consult the IB to determine the relationship. Alternative causes, such as underlying disease(s), concomitant therapy, and other risk factors, as well as the temporal relationship of the event to study drug administration will be considered and investigated.

AEs classified as unrelated or unlikely related will be considered not related to treatment, and AEs classified as possibly, probably, or definitely related will be considered related to treatment.

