7.2.5. Adverse Event Reporting

The Investigator is to report all AEs, whether volunteered by the participant, discovered through questioning, or directly detected, that occur in the time period specified in [Section 7.2.4](#) and according to classifications described in [Section 7.2.3](#).

Non-serious AEs that do not require immediate reporting are to be reported on the AE eCRF. SAEs and AESIs will be reported on the SAE Report Form (see [Section 7.2.6](#)).

Clinically significant AEs such as SAEs, AEs leading to study drug discontinuation/study withdrawal (e.g., based on stopping criteria in [Section 6.1](#)), DLTs ([Section 6.1.1](#)), and AESIs ([Section 7.2.8](#)) that are considered at least possibly related to study drug will be reported to the DMC on an ongoing basis.

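### Protocol 6.1.7 reports every clinically significant AE to the DMC on an ongoing basis, but 7.2.5 attaches a relatedness condition, so ongoing reporting of events judged unrelated is uncertain

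*Protocol*

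**What the plan says.** Three places in the protocol describe which events receive DMC attention.

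- **Section 6.1.7** defines the class broadly: "Clinically significant AEs include but are not limited to SAEs, AEs leading to study drug discontinuation/study withdrawal", followed by DLTs and AESIs. It then states: "The occurrence of any clinically significant AE will be reported to the DMC on an ongoing basis". Causality plays no part in either sentence.
- **Section 7.2.5** lists the same four kinds of event and the same ongoing reporting, but for those "that are considered at least possibly related to study drug will be reported to the DMC on an ongoing basis".
- **Section 3.1.1** lists the four kinds again, with the qualifier "all considered at least possibly related to study drug) will receive special consideration", and refers the reader to Section 7.2.5.

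Two further provisions bear on the consequence. Section 7.2.3.2 fixes what a relatedness condition leaves out: "AEs classified as unrelated or unlikely related will be considered not related to treatment". Section 6.1.8 gives the cohort rule: "If 2 participants in a cohort meet individual stopping criteria, the entire cohort will be stopped or dose-reduced".

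**The concern.** The relatedness judgement belongs to the investigator, and the study is open-label with no control group against which to test it. Under Table 6 of the protocol, an event may be called unlikely related if it meets two of four criteria. One is that the participant's clinical state could readily explain it. Another is that it does not match a known response to the drug. The first could apply to adrenal insufficiency in patients with CAH. The second could apply to a new toxicity in the first study of the drug in children. Adrenal insufficiency, liver chemistry changes, suicidality, and depression or anxiety are the AESIs listed in Section 7.2.8.

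The value of ongoing reporting is that the DMC can react between meetings, and Section 3.1.1 lets its Chair call an ad hoc meeting. If 7.2.5 is the rule applied, the investigator's attribution decides whether an SAE, AESI or AE discontinuation enters that stream at all. The DMC's recommendation also precedes each new cohort (Section 1.2.1), so its picture of emerging safety should not depend on which section the sponsor happens to follow.

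**Working it through.** No arithmetic applies, and the plan states no figure to reproduce. The check sets the two reporting sentences side by side, category by category, and then looks for any text that settles the difference.

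**Step 1. Compare the rules for an event judged unrelated or unlikely related.**

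| Kind of event | Ongoing report under 6.1.7 | Ongoing report under 7.2.5 | Conflict |
|---|---|---|---|
| SAE | Yes | Not covered | Yes |
| AE leading to discontinuation or withdrawal | Yes | Not covered | Yes |
| AESI | Yes | Not covered | Yes |
| DLT | Cannot arise | Cannot arise | No |

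The last row follows from Section 6.1.1, which defines a DLT as a "Grade 3 or higher treatment-emergent adverse event (TEAE) considered at least possibly related to study drug". An unrelated DLT is excluded by definition.

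**Step 2. Look for a tie-breaker.** Neither section refers to the other as controlling. SAP Section 4 gives the SAP precedence over the protocol, but only for planned analyses, and DMC reporting is not one. Section 3.1.1 leaves the DMC's scope and procedures to a charter that is not among the documents. A charter could set a working rule, but the protocol would still contain two.

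**Step 3. Check the cohort rule.** Section 6.1.8 counts participants who meet individual stopping criteria. The liver chemistry (6.1.2), QT (6.1.4), C-SSRS (6.1.5) and depression or anxiety (6.1.6) criteria do not require the event to be attributed to study drug; only the DLT criterion does. Two participants in one cohort could therefore meet such criteria, with both events judged unrelated, and trigger 6.1.8. Under 7.2.5 neither event would be sent to the DMC on an ongoing basis.

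**Step 4. Check the other routes to the DMC.**

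- Section 3.1.1 has the DMC reviewing available data throughout the study and before each new cohort.
- Section 3.1, on the combined review of Cohorts 4 and 6, adds all other available safety data to the sentinel data.
- Section 8.3.4 has the DMC reviewing accumulating safety information by cohort.

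None of these carries a causality filter. None says expressly that events judged unrelated are included, and only the Cohort 4 and 6 text reaches explicitly beyond the sentinels to everything available.

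**Step 5. Bound the delay.** Section 3.1.1 plans three DMC reviews for Cohorts 1-3 and three for Cohorts 4-9, tied to cohort progress and not to the calendar, so no interval can be computed for the treatment periods. Section 3.1.3 sets a 6-month interval once all participants are in the extension. In that phase, if 7.2.5 were applied and no ad hoc meeting were called, an event judged unrelated could wait up to about 6 months.

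**The case against.** The strongest reply is that two data streams must be kept apart. Sections 6.1.7 and 7.2.5 govern reporting as events occur. Cohort decisions rest on the reviews described in Sections 3.1, 3.1.1 and 8.3.4, which are not restricted to related events. A reader might infer that the DMC recommends a higher dose in children without seeing SAEs and AESIs called unrelated. The documents do not support that; such events may simply arrive at the next review. This part of the reply stands and limits the point to ongoing reporting.

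A reader might also put a number on it: with a minimum of 4 sentinels per review in Cohorts 4-9, one missing event would concern a quarter of those reviewed. That does not measure the defect. Nothing withholds a sentinel's own event from the review of that sentinel's data, and the minimum for Cohorts 1-3 is 2, not 4.

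Third, Section 3.1.1 might be taken as a second filter. Its sentence says which events deserve special consideration, after stating that the DMC advises on any trends or safety issues. It sets emphasis and does not limit what is sent.

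Fourth, sites are not left in doubt about their own duty: Section 7.2.6 has them report all SAEs to the sponsor within 24 hours whatever the causality, and AESIs on the same form. That stands too. The uncertainty lies in what goes on to the DMC.

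Finally, 7.2.5 does not contain the word only, so the two sentences can be reconciled by treating it as a partial statement of 6.1.7. But the relatedness condition would then do no work, and anyone following the adverse event reporting section alone would apply it.

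**Conclusion.** The inconsistency is real and confined to ongoing reporting. For three of the four named kinds of event (SAEs, AESIs, and AEs leading to discontinuation or withdrawal), 6.1.7 and 7.2.5 give different answers when the investigator judges the event unrelated or unlikely related. The likely effect is delay or uncertainty in what the DMC receives between scheduled reviews. Loss of these events from escalation reviews is not shown.

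The mismatch with 6.1.8 adds some weight, because events that can stop or dose-reduce a cohort need not have been sent to the DMC as they occurred.

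The conclusion assumes that the relatedness condition in 7.2.5 applies to all four kinds of event, which the parallel wording in 3.1.1 supports, and that the unseen charter does not already require full ongoing reporting. If it does, practice would be sound, but the protocol text would still need correcting.

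**What to change.** - In Section 7.2.5, delete the relatedness condition from the DMC reporting sentence so that it matches 6.1.7. All SAEs, AEs leading to discontinuation or withdrawal, DLTs and AESIs then go to the DMC on an ongoing basis, with the investigator's attribution shown as a data item.
- In Section 3.1.1, make clear that the special-consideration wording sets emphasis within what the DMC reviews and does not filter what it is sent.
- Align the DMC charter with the single rule.

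The DMC can still weigh events by attribution, so no information is lost. The cost is an amendment to protocol wording and slightly more DMC reporting in a study of up to about 70 participants. No assessment, visit or analysis changes.
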